## 2.2 Analysis sets

**Randomized set (RAN)** : All patients who are randomized and not misrandomized if identified from IRT and who did not experience any important protocol deviation related to informed consent.

**Full analysis set (FAS)** : FAS will be comprised of all patients from Randomized set who take at least one dose of study treatment during the treatment period and whose baseline parasitaemia count is greater than 0. Following the intent-to-treat principle, patients will be analyzed according to the treatment group assigned to at randomization.

**Safety set (SAF set)** : Safety set includes all patients who take at least one dose of study drug during the treatment period. Patients will be analyzed according to treatment received.

**Per-protocol set (PPS)** : PPS will be comprised of patients in FAS who

- did not have any important protocol deviations
- took at least 80% of assigned study medication(s). If a patient vomited the original dose but did not vomit the replacement dose, the patient is considered as taking the dose of study medication. Except for patients who are assigned to Coartem treatment, this requires that all patients take all KAE609 dosages as assigned. For Coartem, the patient needs to take at least 5 doses of study drug to have taken 80%.
- did not take other antimalarial medications prior to Study Day 29 for reasons other than rescue medication given for *P. falciparum* related treatment failure, and
- met at least one of the following criteria: (a) classified as treatment failure before Study Day 8 (see [Section 2.1.1.1](#)), (b) absent from parasitaemia at Study Day 29, or (c) had valid PCR evaluations at baseline and at the time point with parasitaemia if parasitaemia is present at Study Day 8 or later.

Important protocol deviations for exclusion from PPS are specified in Table 5-9 and all other important protocol deviations will be identified by the clinical team before the final database lock.

**PK analysis set :** All subjects in the safety analysis set who had evaluable PK parameter data and with at least 80% compliance to study medication and who did not experience any important protocol deviation as mentioned in Table 5-9.

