5.5.6 Rescue medication

The following circumstances warrant discontinuation of study treatment and the implementation of rescue medication (see [Section 6.5.8](#)):

Early treatment failure (ETF)

ETF is defined within this protocol as:

1. Clinical decline or lack of improvement (per Investigator) at 24 hours after first dose of treatment.
2. Development of any clinical complications (described in the WHO definition of complicated/severe malaria (WHO Guidelines 2010)) in the presence of parasitaemia within 72 hours of the first dose of treatment
3. Parasitaemia $> 75\ 000/\mu\text{L}$ at or after 12 hours post-dose
4. Parasitaemia \geq baseline with or without fever at 36 hours after first dose of treatment
5. Any parasitaemia based on microscopy with fever, 48 hours post-dose
6. Parasitaemia $> 100/\mu\text{L}$ based on microscopy with or without fever, 72 hours post-dose

Late Clinical Failure (LCF)

Development of danger signs or severe malaria on any day between Study Day 5 and Day 29 in the presence of parasitaemia without previously meeting any of the criteria of ETF.

Presence of parasitaemia and axillary temperature $\geq 37.5^\circ\text{C}$ on any day between Study Day 5 and Day 29 without previously meeting any of the criteria of ETF.

Late Parasitological Failure (LPF)

Presence of parasitaemia on any day between Study Day 5 and Day 29 and axillary temperature $< 37.5^\circ\text{C}$ without previously meeting any of the criteria of ETF or LCF.

Commencement of rescue medication with Coartem may occur after start of trial medications and up to Study Day 28 as deemed necessary by the investigator. Any patient on KAE609 who

did not need rescue medication up to Study Day 28, will be given Coartem at end of the study at Study Day 29. Rescue medication according to local guidance will be used for severe malaria.

Patients randomized to Coartem and meeting treatment failure definition will be further treated by rescue medication as per local treatment guidance.

The patients receiving rescue medication will not be replaced and will not discontinue the study (i.e., all the examinations as per the assessment schedule and all CRF pages for this patient will need to be completed).

Safety blood tests (Full Blood Count (FBC) and blood chemistry) will be collected on the initial day of rescue medication dosing. Blood films and blood sampling for parasite count and genotyping must be taken before giving the rescue treatment.

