9.1 Analysis sets

Randomized set

All patients who are randomized.

Full analysis set (FAS)

FAS will be comprised of all patients from Randomized set who take at least one dose of study treatment during the treatment period and whose baseline parasitaemia count is greater than 0. Following the intent-to-treat principle, patients will be analyzed according to the treatment group assigned to at randomization.

Safety set (SAF set)

Safety set includes all patients who take at least one dose of study drug during the treatment period. Patients will be analyzed according to treatment received. Full details will be described in the statistical analysis plan (SAP).

Per-protocol set (PPS)

PPS will be comprised of patients in FAS who

- did not have any important protocol deviations
- took at least 80% of assigned study medication(s). If a patient vomited the original dose but did not vomit the replacement dose, the patient is considered as taking the dose of study medication. Except for patients who are assigned to Coartem treatment, this requires that all patients take all KAE609 dosages as assigned

- did not take other antimalarial medications prior to Study Day 29 for reasons other than rescue medication given for *P. falciparum* related treatment failure, and
- met at least one of the following criteria: (a) classified as treatment failure before Study Day 8 (see [Section 6.5.8](#)), (b) absent from parasitaemia at Study Day 29, or (c) had valid PCR evaluations at baseline and at the time point with parasitaemia if parasitaemia is present at Study Day 8 or later.

Important protocol deviations for exclusion from PPS will be identified by the clinical team before the final database lock.

PK analysis set

All subjects in the safety analysis set who had evaluable PK parameter data and took at least 80% of assigned study medication.

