### **2.7.1 Secondary endpoints**

All efficacy analyses are secondary. Secondary efficacy variables include:

- PCR-corrected ACPR at Study Days 15 and 29;
- Uncorrected ACPR at Study Days 15 and 29;

- Proportion of patients with parasitaemia at 12, 24, and 48 hours after the first dose of study drug;
- Parasite clearance time (PCT), defined as time from the first dose until the first total and continued disappearance of asexual parasite forms which remained at least a further 48 hours;
- Fever clearance time (FCT), defined as time from the first dose until the first time the axillary body temperature decreased below and remained below 37.5°C axillary or 38.0°C oral/tympanic/rectal for at least a further 24 hours;
- Proportion of patients with ETF;
- Proportion of patients with LCF;
- Proportion of patients with LPF;
- Incidence rate of recrudescence and reinfection at Study Day 29.

Analyses of ACPRs (PCR corrected or uncorrected) will be based on the FAS and PPS. Analyses of other secondary efficacy variables will be based on the FAS.

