## 5.6 Rule of exclusion criteria of analysis sets

**Table 5-9 Protocol deviations and non-PD criteria leading to exclusion from analysis sets**

Analysis Set	PD (Description and ID) that causes Subjects to be excluded	Non-PD criteria that cause Subjects to be excluded
Randomized	
 
Informed Consent for study participation not obtained and subject entered trial (INCL06)
 
	
 
Not randomized
 
Misrandomized if identified from IRT
 

FAS	NA	
 
Not in Randomized set;
 
Baseline parasitaemia count is 0 or missing
 
No study drug taken
 

PPS	
 
Parasite specie is other than Plasmodium falciparum OR mixed infection (EXCL01)
 
Baseline plasmodium falciparum parasite count <500/uL or >50000/uL at screening visit (INCL03)
 
No fever within the past 24 hours at baseline (INCL04)
 
Received non-study concomitant antimalarial drugs between Day 1 and Day 29 without experiencing treatment failure (COMD02)
 
Patients who received concomitant prohibited medication which found to change the exposure that impacts efficacy. (COMD01b)
 
	
 
Not in FAS;
 
<80% of randomized study medication taken
 
Not classified as non-responder before Day 8, no positive blood smear parasite on Day 8 onwards, and blood smear parasite result is missing at Day 29.
 
Not classified as non-responder before Day 8, have at least one positive blood smear parasite result between Day 8 and Day 29 which cannot be determined as recrudescence or new infection based on PCR genotyping;
 

SAF	NA	
 
Not in Randomized set;
 
No study drug taken
 

PK	Patients who received concomitant prohibited medication which found to change the exposure that impacts interaction in PK parameters (COMD01c)	
 
Not in SAF
 
No evaluable pharmacokinetic parameter data
 
<80% of randomized study medication taken
 

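### The per-protocol dose rule has no exemption for early treatment failure, so multi-day patients stopped for failure before their last required dose are excluded, while single-dose patients with the same failure stay in as non-responders

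*SAP*

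**What the plan says.** SAP 2.2 and Protocol 9.1 define the PPS by a list of conditions joined by 'and'.

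- **Dose rule.** The threshold is 80% of assigned medication. For KAE609, SAP 2.2 states: "Except for patients who are assigned to Coartem treatment, this requires that all patients take all KAE609 dosages as assigned". Protocol 9.1 agrees: "this requires that all patients take all KAE609 dosages as assigned". SAP 2.2 adds: "For Coartem, the patient needs to take at least 5 doses of study drug to have taken 80" percent.
- **Denominator.** SAP 2.4.1 divides doses administered by the planned number for the arm.
- **Exclusion table.** SAP Table 5-9 removes from the PPS anyone with less than "80% of randomized study medication taken". It makes no exception for treatment failure.
- **Failure clause.** The last PPS condition can be met by clause "a) classified as treatment failure before Study Day 8", among other routes.
- **Stopping.** Protocol 5.5.6 introduces the failure definitions, ETF first, with: "The following circumstances warrant discontinuation of study treatment and the implementation of rescue medication". Protocol 5.6.2 also lists lack of therapeutic effect among the reasons for stopping study drug.
- **Use of the set.** SAP 2.7.1: "Analyses of ACPRs (PCR corrected or uncorrected) will be based on the FAS and PPS".

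**The concern.** Being stopped for ETF is itself a bad outcome. If stopping also makes a patient non-compliant under the dose rule, the patient is removed from the PPS because of the outcome that the PPS analysis is meant to count. This can happen only in arms where doses are still due when failure is recognised: the three 3-day KAE609 arms (10, 25 and 50 mg) and Coartem. In the six single-dose arms dosing is complete at time 0, so the same failure cannot affect compliance.

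Per-protocol ACPR would then be too high in the multi-day arms only, and a reader comparing columns could credit repeated dosing or Coartem with cure that comes from the exclusion rule.

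This looks like an oversight. Clause (a) exists to keep failures before Day 8. The antimalarial condition spares rescue given for failure. In Table 5-9, the deviation for non-study antimalarials (COMD02) applies only to patients without treatment failure, and the two exclusions for missing blood-smear or PCR data spare those already classified as non-responders before Day 8. The dose rule alone lacks such protection.

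**Working it through.** **Step 1. Reproduce the plan's own dose threshold.** Minimum doses = 0.80 × planned doses, rounded up.

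- Coartem: 0.80 × 6 = 4.8, so 5 doses (5/6 = 83.3%; 4/6 = 66.7% fails). This matches SAP 2.2.
- KAE609 for 3 days: 0.80 × 3 = 2.4, so 3 doses. This matches the all-doses statement.
- KAE609 single dose: 0.80 × 1 = 0.8, so 1 dose.

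**Step 2. Share of planned doses taken when dosing stops.** Coartem times (0, 8, 24, 36, 48, 60 h) are in Protocol 5.5.4. KAE609 clock times are not stated there; 0, 24 and 48 h is assumed from once-daily dosing for 3 days. ETF criteria are in Protocol 5.5.6 and SAP 2.1.1.1.

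| ETF acted on at | Single dose | KAE609 3-day | Coartem | Multi-day patient in PPS? |
|---|---|---|---|---|
| 12 h (count above 75 000/µL, from 12 h on) | 1/1 | 1/3 = 33% | 2/6 = 33% | No |
| 24 h (clinical), before the dose due | 1/1 | 1/3 = 33% | 2/6 = 33% | No |
| 36 h (count at or above baseline) | 1/1 | 2/3 = 67% | 3/6 or 4/6 = 50% or 67% | No |
| 48 h (parasites with fever), before that dose | 1/1 | 2/3 = 67% | 4/6 = 67% | No |
| 48 h, after that dose | 1/1 | 3/3 = 100% | 5/6 = 83% | Yes |
| 72 h (count above 100/µL) | 1/1 | 3/3 = 100% | 6/6 = 100% | Yes |

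The single-dose patient passes the dose rule in every row, is not excluded for taking rescue after failure, meets clause (a), and is counted as a non-responder.

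**Step 3. Effect on the rate.** Let N be arm size, R responders, and k the failures stopped before the last required dose, with no other PPS exclusions.

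- With failures kept: R/N.
- As written, multi-day arm: R/(N-k).
- Inflation: R/(N-k) - R/N = Rk / [N(N-k)], which is above zero whenever k > 0 and R > 0.

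Arm sizes are planned: 10 for 10 mg × 3 days and for each Coartem arm, 20 for 25 mg and 50 mg × 3 days. The values of k and of late failures are **assumed**. Late failures run from none to about 36% of the remaining patients (the recrudescence figure quoted in Protocol 3.6), rounded to whole patients.

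| N | k | Late failures | R/N | R/(N-k) | Inflation (points) |
|---|---|---|---|---|---|
| 10 or 20 | 0 | any | same | same | 0 |
| 10 | 1 | 0 | 9/10 = 90.0% | 9/9 = 100% | 10.0 |
| 10 | 1 | 3 | 6/10 = 60.0% | 6/9 = 66.7% | 6.7 |
| 10 | 3 | 0 | 7/10 = 70.0% | 7/7 = 100% | 30.0 |
| 10 | 3 | 3 | 4/10 = 40.0% | 4/7 = 57.1% | 17.1 |
| 20 | 1 | 0 | 19/20 = 95.0% | 19/19 = 100% | 5.0 |
| 20 | 1 | 7 | 12/20 = 60.0% | 12/19 = 63.2% | 3.2 |
| 20 | 3 | 0 | 17/20 = 85.0% | 17/17 = 100% | 15.0 |
| 20 | 3 | 6 | 11/20 = 55.0% | 11/17 = 64.7% | 9.7 |

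**Step 4. How likely is k ≥ 1?** The chance is 1 - (1-p)^N for an assumed proportion p stopped early for failure.

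| p | N=10 | N=20 |
|---|---|---|
| 5% | 40% | 64% |
| 10% | 65% | 88% |
| 25% | 94% | over 99% |

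The only related evidence is in Protocol 3.6. An earlier study had three ETFs at 10 mg (42%), one at 20 mg (25%), and none at 15 or 30 mg. Those percentages imply about 7 and 4 patients, and they count all ETFs, not only those acted on before a last required dose.

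**The case against.** The strongest reply is that little depends on the PPS. ACPR is secondary and descriptive; Protocol 9.5 and SAP 2.7 rule out statistical comparison with Coartem for secondary variables. ACPR is also reported on the full analysis set, the Kaplan-Meier ACPR uses only that set, and the ETF proportion is tabulated there by arm with an exact interval. A gap between PPS and full-set results would therefore be visible and explainable. Escalation rests on liver tests, and the primary endpoint uses the safety set. All of this stands and limits the importance of the point.

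Three stronger readings are tempting but not supported.

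- *A reader might infer that every early failure is lost from the 3-day arms.* Failures at 72 h stay in. At 48 h the failure criterion coincides with the third KAE609 and fifth Coartem doses, and the documents do not fix which comes first.
- *A reader might infer a large artificial advantage for 3-day dosing.* The 15-point row (N=20, k=3) rests on assumed counts. The 20-patient 3-day arms are 25 and 50 mg, and the earlier study had no ETF at 30 mg. The 42% figure belongs to 10 mg, whose 3-day arm has 10 patients.
- *A reader might infer that a planned single-versus-repeated-dose efficacy test is biased.* No such test is planned; the distortion affects only an informal reading across arms.

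Conversely, the entry in the SAP document history about removing a PPS analysis does not dispose of the point. It refers to Section 2.3.2 (baseline characteristics), and Section 2.7.1 still plans ACPR on the PPS.

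**Conclusion.** The point holds as a drafting gap in a supportive analysis set. Applied as written, the dose rule removes multi-day patients because they failed, while clause (a) keeps single-dose patients with the same failure. The direction is certain: per-protocol ACPR in the three 3-day KAE609 arms and in Coartem can only be inflated by this route. The size depends on k and may be nil; one such patient adds about 3 to 5 points in a 20-patient arm and about 7 to 10 in a 10-patient arm. Of the KAE609 arms, 10 mg × 3 days is the most exposed, because it is small and the earlier ETF proportion was highest at 10 mg.

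This assumes KAE609 dosing at 0, 24 and 48 h, that investigators stop dosing once ETF is met, and that ETF counts as non-response. The general ACPR definition in SAP 2.1.1.1 supports the last, although the Day 15/29 definitions there look for ETF only from Day 5. No primary, escalation or full-analysis-set conclusion is affected. The correction should be made, but the trial's main findings do not depend on it.

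**What to change.** In SAP 2.2 and Table 5-9, and in Protocol 9.1 for consistency, state that PPS compliance is computed against the doses due up to the time treatment failure was met, so that patients stopped for ETF remain in the PPS as non-responders. This changes only the analysis set; dosing and rescue rules stay as they are.

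The SAP history already contains an addendum made after database lock. If this change also comes after lock, record it as such and report, per arm, how many patients it affects. If the definition is left alone, at least report the number excluded from the PPS for this reason by arm.

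The cost is a sentence in each place and a small programming change. Editing Protocol 9.1 needs a formal amendment with ethics approval under Protocol 11.1, so after lock a documented SAP change may be the practical route. The price in results is a less favourable per-protocol ACPR in multi-day arms wherever k > 0.

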### **Uncorrected ACPR at Day X where X=15 and 29**

- A patient is considered as non-responder at Day X if the patient experiences an ETF, LCF or LPF from Day 5 to Day X.
- A patient is also considered as non-responder if the parasitaemia is not cleared by Day X unless the patient discontinues the study prior to Day X without ETF, LCF, or LPF in which case the response is considered as missing.

- A patient is considered as responder (Uncorrected ACPR) at Day X if the patient is not classified as a non-responder at Day X and the patient has a malaria blood film showing absence of parasitaemia at Day X or later if Day X is missing.
- The response for a patient is considered as missing/undertermined if the patient is not classified as a non-responder and the malaria blood film result at Day X is missing and not followed by a subsequent negative result.

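### The single PPS evaluability rule fits only PCR-corrected ACPR at Day 29, yet it also governs uncorrected ACPR and Day 15, where it drops patients whose outcome is known; SAP 2.2 and Table 5-9 disagree on which ones

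*SAP*

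**What the plan says.** Protocol 9.1 and SAP 2.2 define one PPS with the same fourth condition. A patient must meet at least one of three alternatives: "a) classified as treatment failure before Study Day 8", or "b) absent from parasitaemia at Study Day 29, or (c) had valid PCR evaluations at baseline and at the time point with parasitaemia", the last applying to parasitaemia seen on Day 8 or later.

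SAP Table 5-9 restates this as two exclusions for patients without failure before Day 8. One covers patients with "no positive blood smear parasite on Day 8 onwards, and blood smear parasite result is missing at Day 29". The other covers patients who "have at least one positive blood smear parasite result between Day 8 and Day 29 which cannot be determined as recrudescence or new infection".

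Both documents apply this set to all four ACPR endpoints. SAP 2.7.1 says "Analyses of ACPRs (PCR corrected or uncorrected) will be based on the FAS and PPS", and its list includes "Uncorrected ACPR at Study Days 15 and 29" beside the PCR-corrected pair. Protocol 9.5.1 agrees. Neither document has a version of the PPS by visit or by endpoint.

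The outcome definitions in SAP 2.1.1.1 ask for less. Parasitaemia more than 7 days after the first dose makes a patient a non-responder for uncorrected ACPR, with no reference to PCR. A patient not already a non-responder is a responder at Day X if "the patient has a malaria blood film showing absence of parasitaemia at Day X or later if Day X is missing".

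**The concern.** An evaluability condition should remove patients whose outcome for the analysis at hand cannot be determined. This one was evidently built for PCR-corrected ACPR at Day 29. Used elsewhere, it removes patients whose outcome is known.

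- **Uncorrected ACPR.** Genotype is irrelevant to the outcome, yet undetermined genotype is a reason for exclusion. Only failures first seen on or after Day 8 can be lost this way.
- **Day 15 ACPR.** Membership depends on films and genotypes obtained after Day 15, while failures before Day 8 always stay in.

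Selection then depends on the outcome or on later data. A reader comparing FAS with PPS could take the resulting difference for an effect of adherence. The two SAP texts also do not define the same set, so the programmed PPS depends on which one is followed.

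**Working it through.** The documents give no expected ACPR, no rate of undetermined PCR and no rate of missing Day 29 films, so there is no planned figure to reproduce. The check has two parts: applying the rules to each film pattern, and arithmetic on assumed counts.

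**1. Rules applied to film patterns.** All patterns are for patients without failure before Day 8. "Undetermined" in the table means that the positive film could not be genotyped.

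| Pattern | Uncorrected Day 15 | Uncorrected Day 29 | SAP 2.2 | Table 5-9 |
|---|---|---|---|---|
| Day 15 and 22 negative, Day 29 missing | responder | not known | out | out |
| Day 15 negative, Day 22 positive undetermined, Day 29 negative | responder | non-responder | in, by (b) | out |
| Day 15 negative, undetermined positive at Day 22 or 29, Day 29 positive or missing | responder | non-responder | out | out |
| Day 15 positive undetermined, Day 29 negative | non-responder | non-responder | in, by (b) | out |
| Day 15 positive undetermined, Day 29 positive or missing | non-responder | non-responder | out | out |

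Rows 1 to 3 contain known Day 15 responders; rows 2 to 5 contain certain uncorrected non-responders at Day 29. Rows 2 and 4 are where the two texts conflict. In SAP 2.2 the three alternatives are joined by *or*, so a negative Day 29 film is enough. Table 5-9 excludes on the ungenotyped positive alone. Such patients can arise, because protocol 5.5.6 keeps rescued patients in the study with all scheduled examinations.

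**2. Direction.** Let n be the patients otherwise in the PPS, R the responders, k the dropped failures and m the dropped responders.

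- Uncorrected Day 29, PCR exclusion only: the rate goes from R/n to R/(n − k). With R > 0 and k > 0 it can only rise.
- Day 15, loss of known responders only: the rate goes from R/n to (R − m)/(n − m). The change is −m(n − R)/[n(n − m)], which is negative unless every patient is a responder.
- Uncorrected Day 15, both losses: the rate becomes (R − m)/(n − m − k). It rises if m/(m + k) is below R/n and falls if it is above. From 16/20 = 80%: k = 1, m = 1 gives 15/18 = 83.3%; k = 1, m = 4 gives 12/15 = 80%; k = 1, m = 5 gives 11/14 = 78.6%. The net direction is therefore not fixed.

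**3. Size, assumed counts only.** Arm sizes of 10 and 20 are from SAP 1.1. The dropped patients are taken to be ones that the text in use does exclude; under SAP 2.2 a dropped late failure must also lack a negative Day 29 film.

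| Endpoint | All known outcomes kept | One dropped | Two dropped |
|---|---|---|---|
| Uncorrected Day 29, n = 10, late failures dropped | 6/10 = 60% | 6/9 = 66.7% | 6/8 = 75% |
| Uncorrected Day 29, n = 20, late failures dropped | 16/20 = 80% | 16/19 = 84.2% | 16/18 = 88.9% |
| Day 15, n = 10, responders dropped | 8/10 = 80% | 7/9 = 77.8% | 6/8 = 75% |
| Day 15, n = 20, responders dropped | 16/20 = 80% | 15/19 = 78.9% | 14/18 = 77.8% |

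The Clopper-Pearson 95% intervals are far wider than these shifts: 6/10 gives 26.2% to 87.8% and 6/9 gives 29.9% to 92.5%; 16/20 gives 56.3% to 94.3% and 16/19 gives 60.4% to 96.6%.

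**The case against.** The strongest reply is that little rests on this set. ACPR is secondary and descriptive, with no hypothesis and no comparison with Coartem (SAP 2.7, 2.7.2). The FAS analysis keeps these patients and counts undetermined PCR as non-response (SAP 2.7.2.1). The primary ALT/AST analysis uses the safety set, and no escalation rule uses PPS results. All of this stands and limits the severity.

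It can also be said that few patients will be affected. Protocol 5.5.6 requires parasite-count and genotyping samples before rescue treatment, and the Day 29 window opens at Day 26 with no upper limit (SAP 5.1.4). That makes missing data less likely but does not exclude it.

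Three stronger readings are tempting, and the documents do not support them.

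- A reader might infer that every late failure with undetermined PCR leaves the PPS. That is true of Table 5-9 only; under SAP 2.2 a negative Day 29 film keeps the patient in.
- A reader might infer that late parasitaemia will be frequent in the 10-patient arms because their doses are expected to be sub-therapeutic. In protocol 3.6 the figure tied to the 10 mg group is early failure (42%), and early failures are kept by alternative (a). The 36% recrudescence figure for the earlier dose-finding study is not split by dose. Small denominators do make these arms more sensitive to each dropped patient, but no frequency follows.
- A reader might infer that the PPS is biased in one direction throughout. For uncorrected Day 15 ACPR the two effects oppose each other.

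Finally, the SAP document history records removal of a PPS analysis. That entry refers to Section 2.3.2, the baseline summaries; Section 2.7.1 still uses the PPS for ACPR.

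**Conclusion.** The point holds and is minor. One evaluability condition serves four endpoints and fits one of them. In the PPS, certain uncorrected failures can be dropped for want of a genotype that the endpoint does not need, which can only raise the uncorrected Day 29 rate. Known Day 15 responders can be dropped because of later data, which tends to lower the Day 15 rate. SAP 2.2 and Table 5-9 disagree on patients with an ungenotyped late positive and a negative Day 29 film.

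With the assumed counts, one dropped late failure raises the rate by 6.7 points (6/10 to 6/9) or 4.2 points (16/20 to 16/19). One dropped Day 15 responder lowers it by 2.2 points (8/10 to 7/9) or 1.1 points (16/20 to 15/19). These are illustrations, not forecasts. The logical conclusion rests only on the wording of the definitions; the FAS and the primary safety analysis are untouched.

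**What to change.** Replace the fourth PPS condition with one defined by endpoint and day.

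- For ACPR at Day X, require failure by Day X, or a film at Day X, or a later negative film if the Day X film is missing.
- Require valid PCR only for PCR-corrected ACPR, and only for parasitaemia from Day 8 to Day X.
- Write the same rule in SAP 2.2 and Table 5-9, so that patients with an ungenotyped late positive and a negative Day 29 film are treated alike in both.
- Record the departure from protocol 9.1 in SAP Section 4, which now lists no changes. The current SAP version is already dated after database lock, so a change made now should be labelled as post-lock.
- Show the PPS denominator for each endpoint and day.

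The cost is SAP wording and one evaluability flag per endpoint and day, from data already collected. The drawback is that PPS denominators will differ between endpoints, which is why each must be shown.
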